#### **5. Study Intervention/Design**

Patients will be randomized to either:

- (1) In person LCS intervention** - With *Opioid Risk Education*, patients will receive opioid education after completing the validated Opioid Risk Tool (ORT), a detailed substance abuse survey and mental health screening, and Naloxone education. *Therapeutic Intervention* will include the Community Resiliency Model (CRM). *Clinical Pain Coordination* will include directed referrals for complex needs, including mental health and substance use disorders, as needed. In addition to above mentioned 3 intervention components, all patients in the LCS intervention arm will also receive the current standard-of-care. The Community Resiliency Model (CRM) is a noncognitive variant of mindfulness, emphasizing attunement to interoceptive and exteroceptive signaling cues for regulation of autonomic responses to stress (Grabbe, Higgins, Baird, Craven & San Fratello, 2020). CRM was derived from somatic psychotherapy and self-stabilization interventions using body sensation awareness. Body sensation awareness is called introspection and is a key component of mindfulness. Awareness of internal body sensation occurs in the insular cortex and adjacent brain structures, which serve as cerebral centers regulating emotional regulation, empathy, and social interaction (Simmons et al., 2013). Implementing these techniques may preventatively attenuate the immediate impact of stressors. For example, the CRM model has been implemented across several settings and populations and has been associated with improved well-being, resiliency, and physical symptoms (Grabbe et al., 2020; Grabbe et al., 2021; Habimana et al., 2021). CRM skills are introduced over a sixty-to-ninety-minute session, allowing for a brief introduction and application of skills by participants.

- (2) **Virtual LCS intervention** - With *Opioid Risk Education*, patients will receive opioid education after completing the validated Opioid Risk Tool (ORT), a detailed substance abuse survey and mental health screening, and Naloxone education. *Therapeutic Intervention* will include the Community Resiliency Model CRM).. *Clinical Pain Coordination* will include directed referrals for complex needs, including mental health and substance use disorders, as needed. In addition to above mentioned 3 intervention components, all patients in the LCS intervention arm will also receive the current standard-of-care.

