## **6. Procedures Involved**

If the patient meets inclusion criteria, the CRC will visit patient during their preoperative consult or call the referred patient through his/her number listed on Epic. If unable to visit in person and reach through call, the CRC will message patient through the Secure Chat feature on Epic to potentially schedule an e-consent. If informed consent is obtained, they will be enrolled into REDCap for randomization into one of the three groups. A simple number generator, within RedCap, will sequentially randomize participants into control or one of the two intervention arms. After consenting, enrolling, and allocation, research staff will administer a battery of measures on tablets stored in REDCap, or on paper and later transcribed into REDCap to all participants. In the event the participant is unable to complete study measures during the clinic visit they will be emailed a secure link to RedCap to complete the consent form and the study measures.

Those randomized to the intervention will either meet with a Life Care Specialist for 1 hour before surgery, either in person or via Zoom® during their preoperative consult or at another time no later than 24 hours before surgery.

During their follow up visits with the surgical team at Grady Hospital or Emory Orthopaedics scheduled at 2-weeks, 6-weeks, and 3-months postoperatively participants will again be provided a tablet to complete outcome measures. In the event participants cannot physically travel to the clinic, appointments will be conducted over video conferencing and participants will have the option to be emailed the outcome measures to complete. If they are unable to complete the measures via email within 72-hours study staff will call participants to complete measures over the phone. If no response, paper copies of the measures will be mailed to participants with prepaid

**Protocol Title:** Implementing and Evaluating the Effect of Personalized Pain Coaches After Orthopaedic Surgery for Patients with Sports Medicine Injuries to Improve Postoperative Outcomes

---

postage to return them or QR code post cards to complete surveys. There is a one week window for the first follow up visit, two week window to complete measures for the second follow up study visit, and four weeks for the last study visit. Study staff will call participants and offer to video conference with them within 48 hours of surgery to review how to wear the actigraphy device and use the MEMS cap.

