The following data will be collected on the patients:

- Demographics: Name, date of birth, date of admission, gender, ethnicity, body mass index, zip code, insurance
- Health record data: Data abstraction from health records include injury severity score, mechanism, drug screen on arrival, alcohol screen, pre-existing conditions, inpatient complications, surgical time, regional anesthesia, medication received, and opioid medication doses discharged with.
- Comprehensive social determinants of health (SDOH) survey: This measure includes assessments of housing, financial stability, education, community context, intimate partner violence, health literacy, prior personal and family substance use, a validated measure of post-traumatic stress disorder, adverse childhood experiences, and mental illness. This has been utilized in prior research by this team and takes approximately 20-25 minutes to complete.
- Revised Opioid Risk Tool (ORT): The ORT is a self-reported measure used to ascertain a participant's current and future risk of aberrant drug-related behaviors in patients prescribed opioid therapy.(Cheatle et al., 2019; Webster & Webster, 2005) Recently a shortened revised ORT was recently developed and will be used in this study.(Cheatle et al., 2019) Across 9-items, this tool assesses family history of substance abuse, personal history of substance abuse, age range, and current psychological disease. Each endorsement is scored as 1 for a total score ranging from 0 to 9. Scores of 3 or greater are predictive of high risk for opioid use disorder.
- PTSD screener: This screener is a 5-item screening tool used to assess previous exposure to traumatic events and subsequent presence of the DSM-V diagnostic criteria for PTSD.(Prins et al., 2016) Each item respondents report "Yes" to can be scored as a point so that a minimum of 3 points is used in primary care settings to be considered probable PTSD.

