- Opioid utilization: Inpatient and operating room opioid utilization will be extracted from the electronic health record (EHR) by study staff upon participants' discharge from the hospital. Opioid medication dosage will be transformed to a total universal measure known as morphine milligram equivalent (MME). MME will be averaged over the length-of-stay (LOS) for a daily dosage, known as MME/day. Additionally, the study team will review participants' EHR at each study time point up to 3-months to determine MME throughout postoperative recovery and rehabilitation. Medication Electronic Monitoring (MEMS) devices will be used to assess medication utilization and adherence rates. They are Bluetooth enabled caps that fit on standard medicine bottles and record participants' medication utilization. Participants will be dispensed their opioid medication by the pharmacy in the MEMS equipped containers and informed to return their bottle at their next follow up visit.
- Pain numerical rating scale (NRS): The NRS requires respondents to rate the intensity of their pain on a defined scale from 0, "no pain", to 10, "the worst pain imaginable". The NRS is a commonly used pain assessment tool in both clinical practice and

research. (Farrar et al., 2010) However, the NRS is a single static measure of pain and does not capture the biopsychosocial presentations of pain including physical functioning. As such a battery of objective (e.g. actigraphy) and patient-reported outcomes are needed to best ascertain patient participants' pain experiences. Inpatient NRS, which is recorded by the clinical care team throughout each day, will be extracted from the electronic health record (EHR) by study staff upon participants' discharge from the hospital.

- Mindful Attention Awareness Scale: The MAAS is a validated 15-item scale designed to assess a core characteristic of dispositional mindfulness, namely, open or receptive awareness of and attention to what is taking place in the present.

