- Field notes and participant quotes: Field notes are widely recommended in research as a means of documenting needed contextual information and accurately capturing participants' statements in real time. As such study staff will transcribe notes on their encounters with research participants, including summary of interaction and representative quotes from participants.

The LCS will work with the patient to create a pain management plan focused on behavioral education. The LCS interventions can encompass all, but not limited to, the information included below:

- *Opioid Risk Education*
  - Patients will be provided with education about substance misuse and the opioid epidemic
  - Patients will be educated by the LCS on safe methods for disposal of unused pain medications
- *Therapeutic Intervention*
  - The Community Resiliency Model skills
    - Tracking
    - Resourcing
    - Grounding
    - Gesturing
    - Shift and Stay
    - Help Now!
- *Clinical Pain Coordination*
  - The LCS team will work closely with the [name] as well as pain specialists [name], Co-Director of the acute pain service at Grady and [name], Director of the Medication Assisted Opioid Therapy Clinic.
  - LCS will complete the Behavioral pain assessment tool. The Checklist of Nonverbal Pain Indicators (CNPI) is a quick behavioral assessment used by clinicians to assess nonverbal indicators of potential pain patients are in such as grimacing, bracing, rubbing, and restlessness at rest and when moving.

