#### **10. Inclusion and Exclusion Criteria**

We will recruit 150 participants from the orthopaedic sports medicine service at Grady and Emory Healthcare for this study. Individuals between 15–45 years old, scheduled for orthopaedic surgery due to sports medicine injuries (e.g., anterior cruciate ligament tears, meniscus injury, rotator cuff injury, etc.), and those who are actively employed or full-time athletes prior to injury will be eligible. Individuals unable to provide consent, those undergoing revision procedures, individuals without access to an internet connected device, and individuals who are unemployed or retired at time of injury will be ineligible. No one will be excluded from participation based on gender, race, or ethnicity. Individuals who are incarcerated or pregnant will not be eligible. Individuals unable to consent and those unable to communicate in English will be excluded since all surveys are validated in English.

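### Prior opioid users are eligible, but no pre-operative dose is defined and treatment for opioid use disorder has no MME rule, so a few patients can dominate the 3-month EHR opioid outcome

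*Combined protocol and SAP*

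**What the plan says.** **Who can enter.** Section 10 lists its exclusions, beginning "Individuals unable to provide consent, those undergoing revision procedures, individuals without access to an internet connected device, and individuals who are unemployed or retired", and goes on to incarceration, pregnancy and inability to communicate in English. None concerns current opioid use, opioid use disorder or its treatment.

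**What is recorded before surgery.** Section 4 sets a pre-surgery assessment alongside those at 2 weeks, 6 weeks and 3 months, and says in general terms that measures at these points cover opioid consumption. The health-record items in Section 6 include drug screen, pre-existing conditions, "medication received, and opioid medication doses discharged with". No item is a pre-operative opioid dose, and no look-back period is given.

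**What the outcome counts.** Section 6 (Opioid utilization) converts opioid dosage to MME, averages the inpatient part per day of stay, and then has the team "review participants' EHR at each study time point up to 3-months to determine MME throughout postoperative recovery and rehabilitation". It gives no rule for continuing prescriptions or for medication that treats opioid use disorder. Hypothesis 1.2 in Section 2 is narrower: it concerns opioids taken for pain.

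**What differs by arm.** Section 5 gives both LCS arms "directed referrals for complex needs, including mental health and substance use disorders, as needed". The control arm's standard of care contains written or online resources. Section 6 (Clinical Pain Coordination) has the LCS team work with, among others, the "Director of the Medication Assisted Opioid Therapy Clinic".

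**How it is analysed.** Section 19 plans paired t-tests from pre- to post-surgery and mixed models for mean change over time and by demographics. It names no baseline-opioid covariate, transformation or outlier rule. Allocation is simple: "A simple number generator, within RedCap, will sequentially randomize participants into control or one of the two intervention arms".

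**The concern.** There are two separate problems.

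The first is precision. A patient on long-term opioids may carry three months of dose unrelated to the operation into an outcome compared by means. With 150 patients, simple allocation and no defined prior-dose variable, nothing in the plan controls how such patients fall across the arms or takes out their contribution.

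The second is what the outcome measures. If an LCS referral led to opioid-based treatment of a use disorder, and that treatment appeared in the EHR, a literal conversion of opioid dosage to MME would record it as higher opioid use in the LCS arms. Randomisation does not protect against this, because it arises after allocation.

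Opioid utilization is part of Aim 1 and is a stated secondary objective. At stake is whether the outpatient half of Hypothesis 1.2 can be answered.

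**Working it through.** The documents give no MME mean, SD, effect size, power or prevalence, so there is no stated calculation to reproduce.

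**Inputs from the documents.** Total 150 (Section 10); three arms, simple randomisation (Section 6); outcome window to 3 months (Section 6). The allocation ratio is not stated. I assume 1:1:1, giving 100 LCS versus 50 control for Hypothesis 1.2.

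**Assumed inputs.** Other patients: 3-month MME mean 200, SD 150. Prior users: fraction q = 2-5%, taking 30-60 MME/day for 90 days, so D = 2,700-5,400 MME. Dose variation among prior users is ignored.

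**Step 1: standard error of the arm difference.**

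Variance = (1 - q) x 150² + q(1 - q)(D - 200)²; SE = sqrt[variance x (1/100 + 1/50)] = sqrt(0.03 x variance).

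| q | D | Variance | SE (MME) |
|---|---|---|---|
| 0.02 | 2,700 | 22,050 + 122,500 = 144,550 | 66 |
| 0.02 | 5,400 | 22,050 + 529,984 = 552,034 | 129 |
| 0.05 | 2,700 | 21,375 + 296,875 = 318,250 | 98 |
| 0.05 | 5,400 | 21,375 + 1,284,400 = 1,305,775 | 198 |

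With prior users' contribution removed, SE = sqrt(0.03 x 150²) = 26. For scale, a 30% reduction from 200 is 60 MME, which is smaller than every SE in the table.

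**Step 2: one patient.** Adding D to one patient in the pooled LCS group moves its mean by D/100 = 27-54 MME. The same arithmetic applies to a patient newly started on treatment that is counted in MME at those doses.

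**Step 3: simulation.** Setting: 5,000 trials per case, simple 1:1:1 allocation of 150, pooled LCS versus control, log-normal totals with control mean 200 and CV 1, true reduction 30%, unequal-variance test at two-sided 0.05. The continuing dose is added over 90 days.

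| Prevalence | Continuing dose | Power | Estimate in wrong direction |
|---|---|---|---|
| none, or removed | - | 51% | 1.6% |
| 1% | 20 MME/day | 27% | 8% |
| 1% | 60 MME/day | 12% | 28% |
| 2% | 20 MME/day | 18% | 13% |
| 2% | 60 MME/day | 5% | 33% |

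At 2% prevalence, 150 x 0.02 = 3 such patients are expected and the chance of at least one is 95%. If there are three, all fall in the LCS arms with probability (2/3)³ = 30%.

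**Step 4: inpatient MME/day.** With an assumed mean of 40, CV 0.6 and a 20% reduction, power falls only from 53% to 49% at 2% prevalence and 60 MME/day. It reaches 24% only at 5% and 120 MME/day. A per-day average over the stay does not accumulate 90 days of continuing dose.

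**The case against.** The strongest reply is that a baseline is already intended. Section 4 points to opioid consumption before surgery, and Section 19's pre-to-post tests and models of change presuppose one. With a baseline value in the model, a stable long-term user would contribute little change, and the simulation above, a test on 90-day totals, would overstate the loss. This stands in part: a reader should not infer that the plan ignores pre-operative opioid use. But Section 6 never says what the baseline dose is or over what period it is read, so the intent cannot be carried out as written. Pre-existing conditions, drug screen, the revised ORT and the PROMIS misuse scale can flag some prior users but give no dose.

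Second, age 15-45, the employed-or-athlete requirement and the exclusion of revision procedures may keep prior use rare. That is fair, and no document supports a particular prevalence. The 1% rows show that the loss is still material if doses continue at the assumed levels.

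Third, Hypothesis 1.2 is limited to opioids for pain, so medication for a use disorder may already be meant to fall outside the outcome. A reader might infer that the plan scores successful referral as failure by rule. It does not: it gives no rule either way. Referral is made as needed, no pathway into opioid-based treatment is described, and no expected number is given. What stands is an ambiguity that could act against one side only, because directed referral is a component of the LCS arms.

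Fourth, there are other opioid measures. Inpatient MME/day is little affected, and MEMS caps follow the opioid dispensed in study containers. This stands and confines the point to 3-month EHR MME.

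**Conclusion.** The point holds for the 3-month EHR MME outcome. Prior users are eligible by omission, their pre-operative dose is undefined, and no adjustment for it is named. Under the stated assumptions the SE is about 66-198 MME instead of about 26, and one patient can move the pooled LCS mean by 27-54 MME. These figures rest entirely on assumed prevalence, dose, duration and spread, and on an analysis without a baseline dose.

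Two stronger conclusions are tempting and not supported. Prior use does not bias the comparison on average, because allocation is random; it costs precision and allows chance imbalance. Nor is the whole opioid comparison compromised, since the inpatient measure is much less exposed. The treatment-medication issue is a possible arm-related measurement error whose size cannot be estimated from the documents. The change should be made: opioid use is a stated objective and the remedy is cheap.

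**What to change.** Leave eligibility and clinical care as they are, and settle the following before outcome data are examined.

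1. Reconcile Section 4 with Section 6: add to the EHR abstraction all opioid prescriptions in a fixed period before randomisation (for example 90 days) and any treatment for opioid use disorder, recorded identically in all arms.
2. In Section 19, adjust the 3-month MME analysis for prior opioid use, as none versus any and as dose.
3. Align the MME outcome with Hypothesis 1.2: exclude medication prescribed to treat opioid use disorder in all arms and report it separately by arm.

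The cost is a few more fields in a record review already planned, plus the prior-use terms in the model. The limitation is that prescriptions issued outside the two health systems may be missed, so some prior use will be misclassified or under-measured.

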## **7. Data Specimen Banking**

Survey data and wearable device collected data from participants will be de-identified prior to sharing via REDCap exported files. No PHI will be shared and demographic data with less than 5 responses per field will be excluded to ensure privacy. No biological samples will be collected nor banked.

## **8. Sharing of Results with Participants**

Aggregate findings from this work will be shared with participants via email in the form of peer-reviewed publications if requested.

## **9. Study Timelines**

Study will commence upon IRB approval. Individuals undergoing surgery will be referred by their surgeon to the team who will then contact them to screen for eligibility and interest in enrolling. Study staff will meet with participants during their preoperative visit or over zoom to administer baseline surveys. Those randomized to the intervention arms will also meet with the study intervention team member during that visit. Study staff will meet with participants at each of their postoperative visits, 2 weeks, 6 weeks,

and 3 months. Participants will be discharged from the study at 3 months. Enrollment will continue for 1 year after the start of the study (estimated November 2022–November 2023), data collection will be completed 6 months after (estimated May 2024). Data analyses will be completed by November 2024. Study duration for participants is approximately 90 days.

#### **10. Inclusion and Exclusion Criteria**

We will recruit 150 participants from the orthopaedic sports medicine service at Grady and Emory Healthcare for this study. Individuals between 15–45 years old, scheduled for orthopaedic surgery due to sports medicine injuries (e.g., anterior cruciate ligament tears, meniscus injury, rotator cuff injury, etc.), and those who are actively employed or full-time athletes prior to injury will be eligible. Individuals unable to provide consent, those undergoing revision procedures, individuals without access to an internet connected device, and individuals who are unemployed or retired at time of injury will be ineligible. No one will be excluded from participation based on gender, race, or ethnicity. Individuals who are incarcerated or pregnant will not be eligible. Individuals unable to consent and those unable to communicate in English will be excluded since all surveys are validated in English.

#### **11. Population**

Any individual with an orthopaedic sports medicine related injury.

#### **12. Vulnerable Populations**

Our research may involve teenagers between the ages of 15 to 17 years. If so, proper assent and parental consent will be obtained.

#### **13. Local Number of Participants**

150 patient participants

#### **14. Recruitment Methods**

Potential patient participants will be identified during the daily orthopaedic morning report by surgeons and their staff. Additionally, flyers with study information and brief videos on study will be placed in the clinic waiting room areas and provided to potential participants from their surgical teams to contact the study team and let them know study staff may contact them. The CRC will visit patient during their preoperative consult or call the referred patient through his/her number listed on Epic. If unable to visit in person and reach through call, the CRC will message patient through the Secure Chat feature on Epic (MyChart) to potentially schedule an appointment to review eligibility, provide e-consent, and complete study baseline activities before surgery. A member of the research team will conduct the informed consent discussion with patients and will obtain consent using the IRB-approved consent form either in person or through e-consent in RedCap.

If the patient is a minor, the research team member will conduct the informed consent discussion with both the patient and at least one of the parents/legal guardians, and obtain the patient's assent with parental permission using the IRB-approved consent form. This can also be done in person or through e-consent in RedCap.

Informed voluntary consent will be obtained from each subject in a non-coercive manner.

